9.2 WatchPAT ONE Scoring

The scoring method will be produced in accordance with the device operating manual.

10. STATISTICAL ANALYSIS

10.1 Sample size

With a sample size of at least 30, the large amount of within-person data provides high statistical power for all planned analyses, allowing this data set to answer all proposed questions while minimizing study costs and any risk to patients.

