STU#: STU00214445

PROTOCOL TITLE: Low Burden Wearable Sensor System for Diagnosing Obstructive Sleep Apnea Over Multiple Nights: Diagnostic Agreement with Home Sleep Testing

PRINCIPAL INVESTIGATOR:

[name] MD PhD
Chief of Sleep Medicine
Northwestern Memorial Hospital
Professor of Neurology
Northwestern University Feinberg School of Medicine
P: [contact]
Email: [contact]
[name]

Sponsor:

National Heart, Lung, and Blood Institute

Sponsoring company:

Sibel Inc
Representative: [name]., MD, PhD.
[name]
[name]
P: [contact]

Confidentiality Statement

The information in this document contains information that is privileged or confidential and may not be disclosed unless such disclosure is required by applicable laws and regulations. In any event, persons to whom the information is disclosed must be informed that the information is privileged or confidential and may not be further disclosed by them. These restrictions on disclosure will apply equally to all future information supplied to you, which is indicated as privileged or confidential.

STU#: STU00214445

Signature Pages

Principal Investigator(s):

Name: [name] MD PhD
Title: Chief of Sleep Medicine
Northwestern Memorial Hospital
Professor of Neurology
Northwestern University Feinberg School of Medicine
P: [contact]
Email: [contact]
[name]

Date:

Sponsor Company:

Name: [name], PhD
Title: Sibel Health's Chief Operating Officer
[name]
[name]
P: [contact]
Email: [contact]

Date:

STU#: STU00214445

PROTOCOL SUMMARY

| | |
|--|--|
| Protocol Title (Long Title) | Low Burden Wearable Sensor System for Diagnosing Obstructive Sleep Apnea |
| Protocol Number | v.1 |
| Study Duration | 4 to 6 months |
| Setting | Northwestern University and Participant’s Homes |
| Sample Size | A total of approximately 100 subjects may be recruited to achieve at least 30 subjects to complete the study (Home Sleep Testing portion). |
| Main Inclusion Criteria | 
 ● Age >22 years old or older ● Subjects with suspected or confirmed OSA based on history ● Persons with a previous diagnosis of OSA ● Subjects with self-reported symptoms of OSA ● Willingness to give consent and comply with study procedures |

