| Objectives: | 
Analysis of diagnostic yield from multiple nights with ANNE Sleep
 
 ● Analysis of agreement for diagnosis of moderate to severe OSA by determining a patient’s Apnea-Hypopnea Index (AHI) wearing the ANNE Sleep system and WatchPAT ONE over one (1) night worn concurrently ● Assessment of usability compared to current HST in the intended population |
| Investigational Product and Planned Use | ANNE™ Sleep System |
| Commercial Available HST Device | WatchPAT ONE |
| Statistical Analysis | Three subsequent nights will be with the ANNE Sleep system alone. Patient preference will be elicited via psychometric surveys for comfort |

STU#: STU00214445

| | |
|--|---|
| | 
and usability comparing ANNE and a commercially available Home Sleep Test (HST). We expect completion of this aim in 6 months. The apnea-hypopnea index (AHI) will be calculated in ranges of 15 – 30 apnea/hypopnea events per hour for moderate OSA and ≥ 30 apnea/hypopnea events per hour for severe OSA. The oxygen desaturation index (ODI), the hourly average number of desaturation episodes, will also be calculated. With a sample size of at least 30, the large amount of within-person data provides high statistical power for all planned analyses, allowing this data set to answer all proposed questions while minimizing study costs and any risk to patients.
 |
|--|---|

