4.1 Primary Outcome Measures

- Analysis of variation between nights of AHI derived from ANNE Sleep system across multiple sleep nights at home
- Analysis of agreement for diagnosis of moderate to severe OSA by determining a patient's Apnea-Hypopnea Index (AHI) wearing the ANNE Sleep system and WatchPAT ONE over one (1) night worn concurrently
- Patient responses on psychometric surveys for comfort and usability comparing ANNE Sleep and WatchPAT ONE

•

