5.1.1 Inclusion Criteria

1. ≥22 years old
2. Subjects with suspected OSA based on history and physical. Subjects with self-reported symptoms of OSA based on the STOP-Bang questionnaire indicating affirmative answers to any of the following: snoring, daytime fatigue/sleepiness/tiredness, partners who have observed the subject stopping breathing or choking/gasping during sleep. Persons with a previous diagnosis of OSA are also eligible.
3. Willingness to give written consent and comply with study procedures

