8.1.2 Initial Visit Day: Screening/Enrollment

The subject will have the option to discuss with the study coordinator over the phone or by a Zoom teleconference from the subject's personal device. If Zoom communication is selected a unique meeting number and password known only to the subject will be provided. The study coordinator will monitor the number of attendees in the meeting and restrict meetings to IRB approved researchers on this study, the study subject, and additional people at the subject's discretion. Researchers will host the Zoom sessions and will utilize the waiting room feature to ensure that only the appropriate participants are included on the call.

The study coordinator will cover following topics associated with the study during the Screening/Enrollment visit:

STU#: STU00214445

- (1) Informed Consent will be reviewed and signed electronically using REDCap.
- (2) The qualified subject will be asked to schedule a study date to participate at home. The nights of sensor wear do not need to be consecutive. Subjects will be instructed to set-up both devices on Night One of sleep testing and then only the ANNE device on Nights 2-4.
One Night = HST and ANNE Sleep
3 Additional Nights = ANNE Sleep only
The target time frame will be to complete the sleep nights within 8 weeks of enrollment.
- (3) Subjects will be advised to avoid alcohol and sleep medication use such as antihistamine (OTC) or prescribed medicines for sleep support on the testing night. Any use of these substances on the night of monitoring sleep will be asked to be recorded in the diary.
- (4) Subjects will be informed how to complete the Demographic, Medical History and Sleep Survey sleep diary and usability survey (**Appendix A-C**). The surveys should be available to complete via an email link through REDCap or printed out forms.

Any subject's questions or concerns associated with the study will also be addressed.

At least 24 hours prior to the subject's sleep nights, the study coordinator will contact the participant by phone to confirm their planned sleep study nights at home.

The below sections describe the procedures for setting up the ANNE and HST devices, respectively.

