8.2 COMPLETION OF THE STUDY

- (1) After completing data collection, subjects will be given surveys (**Appendix C**) to complete in print material or by email link via a secure online platform managed by Northwestern University (i.e. REDCap).
- (2) Once the surveys and sleep nights are complete, the study coordinator will let the subject know that their participation is complete. The study coordinator will have a phone call with the subject to confirm testing was successful and address any issues if needed.
- (3) Subjects will be instructed to arrange for a time to return the study kit to the research team in person or will be provided with a pre-paid shipping label. A compensation gift card will then be mailed to the subject’s home address or given to them in-person (if they return the study kits in person to the research team).

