7.1.4 Checklist for scheduled events

The study coordinator should review the schedule of events, summarized below:

| | Initial Visit Day: Screening/ Enrollment | ANNE™ and HST Night One | ANNE™ ONLY Night Two, Three, and Four | End of Study* |
|--|---|-----------------------------------|---|---------------|
| Eligibility | X | | | |
| Consent | X | | | |
| Demographics, Medical Hx, STOP-BANG Questionnaire | X | | | |

STU#: STU00214445

| | | | | |
|---|--|---|---|---|
| ANNE™ Sleep | | X | X | |
| HST Sleep | | X | | |
| Sleep Diary | | X | X | |
| Phone follow-up (which may occur up to 1 week after the study) | | | | X |
| Usability Survey | | | | X |
| Adverse Events | | X | | X |

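### The claim of high power for all analyses rests on repeated nights that inform only one of the three primary outcomes; for device agreement and usability it is unsupported

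*Combined protocol and SAP*

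**What the plan says.** Section 10.1 is one sentence. It sets a sample size of at least 30 and says that "the large amount of within-person data provides high statistical power for all planned analyses". The consequence it draws from this is put as "allowing this data set to answer all proposed questions while minimizing study costs and any risk to patients". The Protocol Summary repeats the sentence under Statistical Analysis. The Sample Size row of the summary says that "approximately 100 subjects may be recruited to achieve at least 30 subjects to complete the study", and ties completion to the home sleep testing portion.

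Section 4.1 lists three primary outcomes: between-night variation of ANNE AHI, agreement on moderate-to-severe OSA "wearing the ANNE Sleep system and WatchPAT ONE over one (1) night worn concurrently", and survey responses on comfort and usability comparing the two devices.

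Section 8.1.2 puts both devices on Night One only, followed by "3 Additional Nights = ANNE Sleep only". In section 9.1 three technicians score each ANNE recording, but their results reduce to one AHI, either by averaging or by a physician's final determination.

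On surveys, section 8.2 says "After completing data collection, subjects will be given surveys" and points to Appendix C. That appendix holds demographics, history and a sleep diary; the sensor survey is Appendix B. The checklist in section 7.1.4 marks the usability survey in the End of Study column alone ("Usability Survey | | | | X"). Section 11 pays for nights together with their corresponding surveys.

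**The concern.** The argument from within-person data depends on repeated measurement, and the repetition is confined to ANNE. A second, third or fourth ANNE night adds no WatchPAT ONE reading, so it adds no agreement pair. Nor do the three scorers, since their scores become one value per recording. The usability survey is scheduled once.

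A reader told that about 30 subjects can settle every question could take an observed sensitivity of 90% as firmly established. Little in the analysis text would correct that. Sections 9.1, 10.2 and 10.3 ask for no confidence interval on accuracy, sensitivity, specificity, PPV or NPV. Intervals are mentioned only for the Bland-Altman analysis (sections 9.1 and 10.3), and the wording does not make clear which quantity they apply to.

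**Working it through.** **Can the stated property be reproduced?** No. The documents give no alpha, numerical power, effect size, SD, intraclass correlation, prevalence, margin or target precision, so no power formula can be run. The check is therefore of precision.

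**What the repeated nights reach**

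| Primary outcome (4.1) | Data per subject | Do nights 2–4 add information? |
|---|---|---|
| Between-night ANNE AHI | up to 4 nights | yes |
| ANNE–WatchPAT agreement | 1 same-night pair | no |
| Usability | 1 survey (checklist, 7.1.4) | no additional survey or WatchPAT night |

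ANNE ODI and the sleep diary are also repeated, but neither is a primary outcome.

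**Diagnostic proportions at 30 completers.** The prevalence of WatchPAT AHI of 15 or more is not given. I assume 30% to 70%, that is 9 to 21 positives, and an observed sensitivity near 90%. The 90% in section 3 is against PSG, so here it is only illustrative. Exact (Clopper-Pearson) 95% limits for x of n are the Beta(x, n−x+1) quantile at 0.025 and the Beta(x+1, n−x) quantile at 0.975. When x = n the lower limit is 0.025^(1/n).

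| Positive share | Sensitivity, 95% CI | Specificity if all negatives agree, lower limit |
|---|---|---|
| 30% | 8/9: 51.8–99.7% | 21/21: 83.9% |
| 50% | 14/15: 68.1–99.8% | 15/15: 78.2% |
| 70% | 19/21: 69.6–98.8% | 9/9: 66.4% |

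The Wilson lower limits for the three sensitivities are 56.5%, 70.2% and 71.1%, so the choice of method matters little to the picture.

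A share above 70% cannot be excluded, because section 5.1.1 adds that "Persons with a previous diagnosis of OSA are also eligible". With 22 positives, 20/22 has an exact lower limit of 70.8%, but only 8 negatives remain, and 7/8 gives 47.3–99.7%.

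Overall agreement of 27/30 gives 73.5–97.9%.

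**Bland-Altman, n = 30 pairs, in units of the SD of the differences**
- Bias: t(29)/√30 = 2.045/5.477 = ±0.37 SD.
- Each limit: t(29) × √(1/30 + 1.96²/58) = 2.045 × 0.3155 = ±0.65 SD.
- If that SD were 5 to 12 events/h (assumed), these are ±1.9 to ±4.5 and ±3.2 to ±7.7 events/h.

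**If all of about 100 recruited complete.** Agreement of 90/100 gives 82.4–95.1%, bias ±0.20 SD and each limit ±0.34 SD.

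**Between-night ANNE AHI.** With n subjects and k nights the within-subject SD has n(k−1) df, and its 95% CI is the estimate times √(df/χ²).
- Four nights each: 30 × 3 = 90 df, factors 0.87 to 1.17.
- Two nights each, a path that section 11 compensates: 30 × 1 = 30 df, factors 0.80 to 1.34.

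Both assume normal within-subject errors with equal variance across subjects, which the plan does not state.

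**Usability.** No figure is offered. No item in Appendix B names WatchPAT ONE, so there is no direct ANNE–WatchPAT scale to size.

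**The case against.** The strongest reply is that the Night One comparison is itself within-person. Each subject wears both devices on the same night, and pairing removes between-subject variation from the bias. That stands. But one pair per subject is not a large amount of data, and nights without the comparator cannot add to it.

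Second, the study is mainly descriptive. Section 10.2 tabulates and summarizes, and with no hypothesis or margin power is undefined. This also stands, and it limits the point: a reader might infer from the wide intervals that the study is underpowered, but no width can be called inadequate when no target is stated. It is equally a reason not to claim high power.

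Third, Bland-Altman with 95% intervals is planned in section 9.1 as well as in the exploratory section 10.3. An interval-based look at agreement therefore does exist outside the exploratory list. What is missing is intervals on the diagnostic proportions and clear Bland-Altman wording.

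Fourth, about 100 may be recruited. The commitment is to at least 30 completers, so expected precision should be shown there; the case of 100 is given above.

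Finally, the number of surveys is not fully settled. The checklist supports one usability survey at the end, while sections 8.2 and 11 speak of surveys in the plural. On either reading, there is only one night with WatchPAT ONE.

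**Conclusion.** The claim is wrong as written. The repeated nights support one of the three primary outcomes. For agreement and usability the assertion of high power has no stated basis, and for between-night AHI it carries no number.

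At 30 completers, with 30% to 70% WatchPAT-positive, the exact lower limit for a sensitivity near 90% is about 52% to 70%. For a perfect observed specificity it is 66% to 84%. The within-subject ANNE SD is known to 0.87–1.17 times the estimate only if all 30 complete four nights. The prevalence, the observed proportions and the error model are my assumptions.

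The count of one pair per subject rests on the documents alone; the count of one usability survey follows the checklist. The point concerns the stated justification and the reporting of uncertainty. It is not evidence that 30 is too few.

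**What to change.** In section 10.1 and the Protocol Summary, remove the assertions that "the large amount of within-person data provides high statistical power for all planned analyses" and "allowing this data set to answer all proposed questions while minimizing study costs and any risk to patients". In their place state that:

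- the repeated nights support estimation of between-night ANNE AHI variation, with the expected CI for the within-subject SD by number of nights completed and its normal, equal-variance assumption;
- agreement is estimation on at least 30 same-night pairs, with expected interval widths and the assumed prevalence of AHI of 15 or more;
- usability is descriptive, with no power claim, once sections 7.1.4, 8.2 and 11 are reconciled on which surveys are given and when.

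In section 9.1, ask for 95% CIs by one named method on accuracy, sensitivity, specificity, PPV and NPV. Clopper-Pearson would match the widths above; another method would serve if named in advance. In sections 9.1 and 10.3, reword the Bland-Altman text to ask for CIs on the bias and on each limit of agreement.

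The cost is a few wording changes and some routine calculations. Enrolment, nights and devices stay as they are. The only downside is a less favourable stated property.

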10.2 Apnea-hypopnea index (AHI) and oxygen desaturation index (ODI)

1. AHI will be calculated in ranges of 15 – 30 apnea/hypopnea events per hour for moderate OSA and ≥ 30 apnea/hypopnea events per hour for severe OSA. Continuous variables of AHIs during ~~three~~four-night study will be summarized using tables of descriptive statistics. The AHIs with variables will be summarized using counts and percentages. Descriptive statistics will be presented by diagnosis.
2. Diagnostic outcomes will be tabulated and compared for ANNE Sleep vs WatchPAT ONE.
3. Patient preference will be elicited via psychometric surveys for comfort and usability comparing ANNE and WatchPAT ONE.

STU#: STU00214445

4. The oxygen desaturation index (ODI), the hourly average number of desaturation episodes, will also be calculated.

10.3 Exploratory measurements for research purposes

Additional statistical analyses will be performed to compare outputs of AHI between the different systems. Specifically, these analyses include:

1. Linear regression to establish correlation between AHI determined by ANNE Sleep vs WatchPAT ONE on the same night. Bland-Altman plots will be created to establish bias and 95% confidence intervals of agreement between AHI determined by ANNE Sleep and WatchPAT ONE.
2. Summary statistics of the sensitivity, specificity and accuracy of the classification of the severity of OSA (normal, mild, moderate, and severe OSA) determined by AHI between ANNE Sleep and WatchPAT ONE.
3. Accuracy analysis between AHI determined by ANNE Sleep vs AHI determined by WatchPAT ONE on the same night.
4. Descriptive analysis of patients' characteristics and assessments (e.g. sleep diary) before and after study procedures. Patient characteristics include age, gender, ethnicity, race, height, weight, baseline vital signs, relevant medical and surgical co-morbidities will be abstracted from the medical record or by direct survey of the participants.
5. The listings, specifically adverse events and major protocol deviations, will be ordered by subject.

11. COMPENSATION FOR PARTICIPATION IN RESEARCH ACTIVITIES

Subjects who complete the at home testing will receive \$100 in gift cards for their time and effort for completing all 4 nights with corresponding surveys. If subjects complete one night with the HST and ANNE and one night with ANNE only, they will receive \$50 in gift cards for their time and effort for completing these 2 nights with corresponding surveys.

Compensation will be given to participants directly or mailed to the participant's home within 4-6 weeks after study completion.

12. WITHDRAWAL OF PARTICIPANTS

Participants may end their participation at any time during the study. The study investigators may choose to withdraw a study subject if he or she is unable to use the devices or complete the study procedures. The study investigators may withdraw a patient if they develop skin sensitivity or have a medical complication that precludes wearing of the sensors on the suprasternal notch.

If a subject is withdrawn from the study, they will be asked to return the study kit that is given to them at the start of the study. Unless specifically requested in writing, researchers will maintain and use data from patients that end their participation early.

13. RISKS TO PARTICIPANTS

STU#: STU00214445

Risk category: minimal

Potential risk: There is a risk of skin irritation, rash, possible injury upon removal of the sensor, or allergic reaction to the ANNE™ Sleep sensors adhesive. The devices will be placed on skin epidermis without conductive gel, thereby minimizing the risk of any skin irritation or allergic reaction. In addition, there will be no skin preparation except the use of a sterile alcohol pad (provided) to gently exfoliate the dead skin cells or dirt on epidermis. The adhesives are silicone based and have passed both biocompatibility, skin sensitization and cytotoxicity testing.

There is a risk of Protected Health Information (PHI) disclosure. Subject data will be de-identified and stored securely to prevent PHI disclosure.

Protection against risks: The sleep sensors can be removed if associated with significant discomfort or rash.

SURVEY/DIARY: Some questions may make subjects uncomfortable or upset. Subjects do not have to answer these questions if they do not want to.

14. ADVERSE EVENTS

The PI will determine whether adverse events are related to the study or unrelated to the study. The length of the study will be 4 nights. All serious adverse events – even if not deemed to be study-related – will be reported to the IRB. This includes a participant's death, life-threatening condition, hospitalization, or disability. All study-related adverse events determined by the PI as serious will be recorded and reported to the IRB and the sponsor within 1 business day. Serious study-related adverse events are defined as adverse skin effects that warrant prescription medical therapy, skin tears leading to bleeding or an open wound, or skin burns. Study-related adverse events will be recorded on the adverse event form. If participation is discontinued, the timing of this will be recorded.

15. DATA MANAGEMENT AND PARTICIPANT CONFIDENTIALITY

Subject identifiable medical information obtained as a result of this study is considered confidential and disclosure to third parties other than the PI and the study team is prohibited. All reports and communications relating to subjects in this study will refer to each subject only by their study identification number. Data generated as a result of this study are available for inspection on request by Food and Drug Administration or other government regulatory agency auditors, Sibel business partners specifically HealthCore, Inc. and the Institutional Review Board (IRB).

Subject identity will be protected through use of a coded list of identifiers which will be maintained separately from the data set. Any paper source documents, questionnaires, and CRFs are kept in a secured area (in a locked cabinet in a locked room) and all electronic data is password protected on a secure NU research server so that only authorized personnel can have access.

STU#: STU00214445

Only authorized research personnel listed on the IRB protocol will have direct access to this data set, although there may be collaborative exchange of de-identified data with other research institutions for assistance in the analysis of raw data.

Data will be capture using NU REDCap, a secure research database. Data stored and used for future research will be de-identified. Data will not be used for future research outside of the scope of this study.

PROTECTED HEALTH INFORMATION (PHI AND HIPAA)

The following PHI will be collected, and is also listed on the consent form for study enrollment:

- Demographic data including name, birthdate, address and phone number
- Results of physical examinations
- Medical history
- Lab tests, or certain health information indicating or relating to a condition as well diaries and questionnaires
- Records about study medication or drugs
- Records about study devices

Entry of any data into a study site clinical record during the duration of the research study is also PHI that may be collected and listed in the consent form. PHI from the above categories may be obtained from the respective study sites and affiliated entities listed as study locations.

Any research information shared with outside entities during the study will not contain the name, address, telephone or social security number or any other personal identifier unless disclosure of the identifier is necessary for review by such parties or is required by law or study site policy except that such information may be viewed by the Study sponsor and its partners or contractors at the Principal Investigator's office.

